## 5. ANALYSIS SETS

### 5.1 Intent-to-Treat Analysis Set

The Intent-to-Treat (ITT) analysis set will include all randomized subjects. In this analysis set, treatment will be assigned based upon the treatment arm to which subjects were randomized regardless of which treatment they receive. ITT analysis set will be used for primary, secondary, and exploratory efficacy analyses.

### 5.2 Safety Analysis Set

The safety analysis set will include all randomized subjects who receive at least 1 dose of imidolimab or placebo. The safety analysis set will be used for all safety analyses. Subjects will be analyzed as treated. If a subject receives both treatments in the placebo controlled period, they will be analyzed in the imidolimab group.

### 5.3 Extension Analysis Set

The extension analysis set is a subset of the safety analysis set who receive at least 1 dose of imidolimab in the extension period. The extension analysis set will be used for summarizing both efficacy and safety data for those subjects who entered the extension period. Subjects will be analyzed as treated.

### 5.4 Per Protocol Analysis Set

The per protocol analysis set will include all subjects in the ITT analysis set who do not have important protocol deviations that would affect the evaluation of the primary efficacy endpoint. Further details on the determination of protocol deviations are described in **Section 7.3**.

### 5.5 Pharmacokinetic Analysis Set

The PK analysis set will include all imidolimab-treated subjects in the safety analysis set who have at least 1 quantifiable post-dose PK sample available and who do not have events or protocol deviations or events

with the potential to affect PK concentrations. The PK analysis set will be used for all PK analyses except that the Safety Analysis Set will be used for all PK analyses during the primary analysis.

The PK Analysis Set will be determined after review of the clinical study data (e.g., concomitant medications, study drug dosing information, and adverse events). Prior to the final PK analysis, subject data as well as protocol deviations will be reviewed in a blinded manner by [REDACTED] and Anapty Bio at the blinded data review meeting (BDRM) for inclusion/exclusion into the PK Analysis Set.

## 5.6 Analysis Sets for Analyses

Demographics will be summarized on the ITT Analysis Set; Per Protocol (PP), PK, Extension, and Safety Analysis Sets will be tabulated only if they are different from ITT Analysis Set for demographics. Extent of exposure, safety, biomarker, and anti-drug antibodies (ADA) data will be summarized on the Safety Analysis Set. Efficacy analyses will be performed on the ITT and (where indicated) PP Analysis Sets.

## 6. SPECIFICATION OF ENDPOINTS AND VARIABLES

Two baselines will be defined: study baseline and imsidolimab baseline. The study baseline will be the last available measurement taken prior to the first dose of study treatment (either imsidolimab or placebo). The imsidolimab baseline will be the last available measurement taken prior to the first dose of imsidolimab. For subjects assigned to placebo in the placebo-controlled period of this study who continue into the extension period, the imsidolimab baseline will be the value prior to receiving the first dose in the extension period.

For numerical values, change from baseline will be calculated as the difference between the value of interest at a specified visit and the corresponding baseline value.

The percentage change from baseline at Week X is defined as:

$$100\% \times \{(\text{Observed value at Week X} - \text{baseline value}) / \text{baseline value}\}$$

### 6.1 Demographic and Baseline Characteristics

#### 6.1.1 Demography and Physical Characteristics

Subject demographics and baseline disease characteristics will be summarized overall as well as by treatment arm in the baseline disease characteristics output.

Demographic and baseline characteristic variables summarized will include the following:

- Age
- Sex
- Race
- Ethnicity (Hispanic or non-Hispanic)
- Country
- Woman of childbearing potential (yes or no)
- Smoking history (never, current, former)
- Prior history of anti-tumor necrosis factor (TNF; Humira) use (yes or no)
- Weight (kg)

- Height (cm)
- Body mass index (BMI; kg/m^2)
- Hurley Stage at randomization
- Fitzpatrick skin type
- Hidradenitis Suppurativa Patient Global Assessment (HS-PtGA) score at baseline
- Dermatology Life Quality Index (DLQI) at baseline
- Hidradenitis Suppurativa Quality of Life (HiSQoL) score at baseline
- Hidradenitis Suppurativa Physician Global Assessment (HS-PGA) score at baseline
- Total abscess and inflammatory nodule (AN) count at baseline
- Total abscess count
- Total inflammatory nodule count
- International Hidradenitis Suppurativa Severity Score System (IHS4) at baseline
- Draining fistula count at baseline
- Worst pain numeric rating scale (NRS) at Baseline (grade 0 to grade 10)
- Average pain NRS at Baseline (grade 0 to grade 10)
- Patient global impression of severity (PGI-S) at Baseline (no activity, mild, moderate, severe)
- Patient global impression of bother (PGI-B) at Baseline

### 6.1.2 Medical and Surgical History

Medical and surgical history will be collected at the Screening visit and will be coded using the version of the Medical Dictionary for Regulatory Activities (MedDRA) specified in the approved Data Management Plan.

### 6.1.3 Prior, Concomitant, and Rescue Medications/Treatments

All medications used to treat HS disease conditions within 6 months prior to Day 1, any prior use of adalimumab (Humira), and all concomitant therapy taken by the patient within 4 weeks prior to enrollment or while on study will be recorded on the Prior or Concomitant Medications CRF page. Use of Humira to treat HS will be identified by concomitant medication records having the World Health Organization Drug Dictionary (WHO-DD) medical coding preferred name “Adalimumab”.

Prior medication/treatment is any medication/treatment stopped prior to the first dose of study treatment. Concomitant medication/treatment is any medication/treatment continued to be taken at the time of the first dose or started after the first dose of study treatment. Prior and concomitant medications are those which start before the first study treatment but are ongoing or which end after first study treatment.

Rescue medications taken by the subject to control intolerable symptoms of HS during the study will be recorded on the Rescue Medication CRF page.

Rescue procedures performed to control intolerable symptoms of HS will be recorded on the HS Procedures CRF page.

**Coding:** Verbatim medication or treatment terms will be coded by [REDACTED] and will be assigned a preferred name and an Anatomical Therapeutic Chemical Class (ATC) term using the version of the WHO-DD specified in the approved Data Management Plan.

**Multiple ATC assignments:** If there are multiple ATC codes assigned to the same concomitant medication, the “primary” one based on a medical evaluation will be used.

**Uncoded Medication:** Before the database lock, uncoded medications/treatments may be assigned the string “UNCODED” as the ATC code, and the verbatim term will be used as the preferred name, so they can be included in the summary tables. In final datasets, all the names will be coded.

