15. Over-the-counter topical antiseptic washes, creams, soaps, ointments, gels, and liquids containing antibacterial agents to treat HS within 2 weeks prior to Day 1 (unless specified as permitted in [Section 6.5.1](#))
16. Systemic non-biologic therapies with potential therapeutic impact for HS within 4 weeks of Day 1, including methotrexate (MTX), cyclosporine, retinoids, and fumaric acid esters, and oral or injectable corticosteroids (unless clearly specified as permitted; see [Section 6.5.1](#)).
17. Oral analgesics (including opioids) within 2 weeks of Day 1, unless a subject is on a stable dose (PRN is not considered a stable dose) of non-opioid analgesics for a non-HS medical condition (eg, osteoarthritis), and the is stable for 2 weeks prior to Baseline and is anticipated to remain stable throughout study participation.
18. Subject requires or is expected to require opioid analgesics during the study for any reason (excluding tramadol as described in [Section 6.5.1](#)).
19. Nonbiologic investigational drug within 4 weeks or 5 half-lives of Day 1, whichever is longer.

20. Biologics for at least 12 weeks or 5 half-lives prior to Day 1 (eg, adalimumab).
21. Live or live-attenuated vaccines within 12 weeks prior to Day 1. Live and live-attenuated vaccines may be utilized 12 weeks after the last study treatment administration Note: Currently authorized non-live and non-live-attenuated vaccines for COVID-19 (eg, RNA-based vaccines, protein-based vaccines, and nonreplicating viral vector-based vaccines) are allowed during the study.
22. Surgical, laser, or intense pulsed light (IPL) intervention in area with HS lesion within 4 weeks prior to Day 1.
23. Phototherapy (psoralen and ultraviolet A [PUVA] and/or UVB) within 4 weeks prior to Day 1
24. Active TB or latent TB infection as indicated by a positive QuantiFERON®-TB Gold test at screening (if the test is indeterminate, it can be repeated only once), chest X-ray, and/or clinical examination, or has had active TB disease at any time in the past.
25. Clinically significant drug or alcohol abuse in the last year prior to Day 1, or other factors limiting the ability to cooperate and to comply with the study protocol, as determined by the Investigator.
26. Subject is a pregnant or lactating woman, or a woman who intends to become pregnant during the study period.

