#### 6.5 CONCOMITANT THERAPY

Any medication or vaccine (including over the counter or prescription medicines, vitamins, and/or herbal supplements) that the subject is receiving at the time of enrollment and receives during the study must be recorded on the eCRF along with:

- Reason for use
- Dates of administration including start and end dates
- Dosage information including dose, route, and frequency

All medications used to treat HS disease conditions within 6 months prior to enrollment, and any prior use of adalimumab (Humira), must be recorded in the eCRF. Any other medications taken within 4 weeks prior to enrollment must also be recorded in the eCRF. Dose adjustments of these treatments should be avoided during the study. Live and live-attenuated vaccines may be utilized after the subjects complete the safety follow-up period of the study. During the follow-up period, no study drug will be administered and 12 weeks (at least three half-lives of study drug) is

estimated to be a sufficient period after the last dose administration when a live or live-attenuated vaccine can be safely administered.

The Medical Monitor should be contacted if there are any questions regarding concomitant or prior therapy.

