### **7.5.5 Subgroup Analyses**

Subgroup analyses will be carried out but only for the primary efficacy endpoint. Each subgroup will be analyzed separately using descriptive statistics. No hypothesis tests will be performed. Subgroup variables that will be examined include:

- Smoking status:
  - Current

- Not Current
- Prior history of anti-TNF (Humira) use for HS indication:
  - Yes
  - No
- AN count at baseline:
  - <= median
  - > median
- Age groups:
  - [18, 65) years
  - [18, 30) years
  - [30, 45) years
  - [45, 65) years
  - [65, 75) years
- Sex groups:
  - Male
  - Female
- Hurley Stage at baseline:
  - Stage II
  - Stage III
- Rescue medication used during the treatment period:
  - Yes
  - No

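### The subgroup for prior Humira use for HS is derived from the drug name alone, so it can include subjects who took adalimumab only for another disease

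*SAP*

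**What the plan says.** Four places bear on this variable.

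- **Label.** SAP 7.5.5 lists a Yes/No subgroup, "Prior history of anti-TNF (Humira) use for HS indication", to be summarised for the primary endpoint only, descriptively and without hypothesis tests.
- **Rule.** SAP 6.1.3 states: "Use of Humira to treat HS will be identified by concomitant medication records having the World Health Organization Drug Dictionary" preferred name Adalimumab. This is the only derivation given.
- **Records collected.** SAP 6.1.3 lists HS medication from the six months before Day 1, and then "any prior use of adalimumab (Humira), and all concomitant therapy taken by the patient within 4 weeks prior to enrollment". Protocol 6.5 has the same structure: HS medication over six months, and separately "any prior use of adalimumab (Humira), must be recorded in the eCRF".
- **Baseline table.** SAP 6.1.1 lists a second variable, "Prior history of anti-tumor necrosis factor (TNF; Humira) use (yes or no"), which is not restricted by indication.

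Protocol 6.5 also names a "Reason for use" field. The sentence that introduces it concerns medication being received at enrollment or received during the study.

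**The concern.** A coded drug name identifies the product, not the disease it was given for. The label in 7.5.5 promises a group defined by indication, and the rule in 6.1.3 cannot deliver one. If past use for other diseases is in the database, as both collection clauses allow, those subjects enter the Yes group under a heading that describes them wrongly.

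What is at stake is how one subgroup row is read. Someone looking at the change in AN count among subjects said to have had Humira for HS would take it as the result in previously biologic-treated HS, and the group could be a mixture. This is a rule that gives the wrong answer for one type of subject, not merely a missing detail.

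**Working it through.** The plan gives no figure to reproduce. The check is to apply the rule as written and compare the result with the label.

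1. **Is there an indication condition anywhere?** I looked in SAP 6.1.3, 7.4.3, 7.5.5 and Appendix 1 (item 7, prior and concomitant medication). None contains one.

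2. **Can non-HS records be in the data searched?** Yes, on the natural reading. Both documents set past adalimumab use apart from HS medication and attach no limit of time or indication to it.

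3. **Can such subjects enrol?** Yes. Exclusion criterion 20 ("Biologics for at least 12 weeks or 5 half-lives prior to Day 1 (eg, adalimumab") imposes a washout and does not bar earlier use for any disease.

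4. **Apply label and rule to each type of subject**, taking the rule to search the combined prior/concomitant medication page:

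| Past adalimumab | Label in 7.5.5 | Rule in 6.1.3 |
|---|---|---|
| None | No | No |
| For HS only | Yes | Yes |
| For HS and another disease | Yes | Yes |
| For another disease only | No | **Yes** |

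The two disagree in the last row only. The error runs one way: it can add subjects to Yes wrongly but cannot remove any.

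5. **The word concomitant.** SAP 6.1.3 classes a drug stopped before first dose as prior. Because of the washout, an eligible subject's past adalimumab is prior. Read literally, a search of concomitant records would miss the very subjects intended. The sentence presumably means the combined CRF page, but it should say so.

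6. **Two variables, one rule.** The name-only rule fits the unrestricted baseline variable in 6.1.1. It does not fit the subgroup in 7.5.5, which adds the indication.

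7. **Size.** If m of the n Yes subjects in an arm are misplaced, they form m/n of that cell. The documents give neither m nor n, and m may be 0. As an illustration only, assume that 10% to 20% of the 120 subjects have an adalimumab record: 120 × 0.10 = 12 and 120 × 0.20 = 24. Spread evenly over three arms that is 12/3 = 4 to 24/3 = 8 per arm. One misplaced subject would then be 1/8 = 12.5% to 1/4 = 25% of an arm's Yes cell. The 10% to 20% is an assumption without support in the documents.

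**The case against.** The strongest reply is that the collection clause can be read narrowly. It opens with medication used to treat HS in the last six months, and the words on adalimumab may be meant only to lift the time limit. On that reading the records collected are HS records, and the rule fits its label. This is possible, but the clause carries no HS qualifier of its own, and a site following it literally would enter every past use.

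It can also be said that few such subjects will enter. Exclusion criterion 8 is now blank, but criteria 1, 2 and 27 still exclude interfering, clinically significant or confounding disease. That stands as a reason to expect small numbers, not as a reason why there can be none.

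A reader might infer more than the documents support:

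- **That the reason for use is already held for every medication, so the repair is one line of code.** Protocol 6.5 ties that field to medication at enrollment and on study. The following paragraph, on past adalimumab, names no fields. Whether the reason exists for washed-out adalimumab has to be checked in the annotated CRF.
- **That users of other anti-TNF agents are wrongly counted as No.** The parenthesis naming Humira already narrows the label in both SAP sections. A group of all anti-TNF agents could not be built reliably either, because HS drugs other than adalimumab are required only for the previous six months.
- **That the subgroup exists to test the unmet-need argument in Protocol 4.2.** SAP 7.5.5 states no purpose. Protocol 4.2 concerns failure to respond to adalimumab, whereas this variable records use.
- **That a definite number, such as 1 to 6 subjects, will be misplaced.** That range needs assumed rates of adalimumab use (10% to 20%) and of non-HS indication (10% to 25%): 12 × 0.10 = 1.2 and 24 × 0.25 = 6. Neither rate is in the documents, and zero is possible.

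**Conclusion.** The point holds as a mismatch between label and derivation. As written, the rule in SAP 6.1.3 can place a subject who took adalimumab only for another disease in the Yes group of a subgroup defined in 7.5.5 by HS indication. This rests on the natural reading of the collection clauses and on there being no indication filter in the annotated CRF or mock tables, which were not available.

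The consequence is small. The subgroup is descriptive, covers only the primary endpoint and carries no test, so the primary analysis, alpha and power are untouched. Past use is fixed before randomisation, so misplacement should not systematically favour an arm. The number affected is unknown and may be zero. It is worth correcting because the correction is nearly free.

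**What to change.** Check the annotated CRF for a reason-for-use field on past adalimumab records. Then take one of two routes.

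- **Reason captured.** In SAP 6.1.3, define Yes as a prior or concomitant record with preferred name Adalimumab **and** HS as the recorded reason. Review the reason text blind before the Week 16 snapshot. Head the row in 7.5.5 as prior adalimumab for HS.
- **Reason not captured.** Delete the indication from the label in 7.5.5 and the words on treating HS from the rule in 6.1.3. Report the subgroup as any prior adalimumab use, consistent with 6.1.1.

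In both cases, replace concomitant with prior or concomitant in the rule. Do not widen the group to all anti-TNF agents, since the six-month limit on other HS medication would leave it incomplete.

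The first route costs one extra condition and a short blinded review; the second costs a few deleted words. Neither needs new data or changes another analysis.

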## 6.2 Efficacy

Endpoints analyzing the placebo-controlled data will use the last pre-dose assessment for all visits and for all study arms. The extension period starts at the Week 16 dose, and endpoints analyzing the extension period data will include pre-dose results from Week 16 as the imidolimab baseline for the placebo arms, as well as pre-dose results from Weeks 20, 24, and 28, and follow-up results (no dose) from Weeks 32, 36, and 40 for all study arms.

### 6.2.1 Study Day and Visit Window Definitions

Efficacy data obtained from unscheduled visits [not including the End of Study visit] will be allocated to the scheduled visit corresponding to the visit window they fall in as specified in **Table 2**. Efficacy data will be analyzed based on the nominal visits and nominal time points. If there is no pre-dose assessment for the window, then the closest post-dose assessment may be used instead. Only if the data from the nominal visit or time point is missing or falls outside the visit window will data from unscheduled visits for the same nominal visit or time point be used in analysis. Unscheduled visits will only be considered for use at an analysis time point if they fall within the respective window. If more than one unscheduled visit exists in a given window, the measurement closest to, but not after, the nominal day will be used in analysis. Efficacy data from scheduled and unscheduled visits will be listed.

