**Table 2 Analysis Visit Windows**

Study Period	Nominal Visit	Nominal Day	Visit Window (day)
Screening	Screening	-30 to -1	-30 to -1
Placebo-Controlled, Double-Blind	Day 1	1	1 (Pre-dose)
	Week 4	29	1 (Post-dose) to 42 (Pre-dose)
	Week 8	57	43 to 70 (Pre-dose)
	Week 12	85	71 to 108 (Pre-dose)
	Week 16	113	109 to 136 (Pre-dose)
Treatment Extension	Week 16	113	109 to 136 (Pre-dose)
	Week 20	141	137 to 164 (Pre-dose)
	Week 24	169	165 to 192 (Pre-dose)
	Week 28	197	193 to 220 (Pre-dose)
	Week 32	225	221 to 248
	Week 36	253	249 to 275

	Week 40	281	276 to 286
--	---------	-----	------------

Study Day and Day of Assessment or Event definitions are provided in **Appendix 1**.

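### The SAP's rule for choosing among several unscheduled visits looks only backward from the nominal day, so it can leave Week 16 without a value when valid counts exist and can prefer a distant early count at Weeks 4, 8 and 12.

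*SAP*

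**What the plan says.** SAP 6.2.1 sets an order of preference for efficacy data. The scheduled visit comes first: "Only if the data from the nominal visit or time point is missing or falls outside the visit window will data from unscheduled visits" be used. The unscheduled value must also lie in the Table 2 window: "Unscheduled visits will only be considered for use at an analysis time point if they fall within the respective window". For a single unscheduled visit there is no further limit. For more than one, "the measurement closest to, but not after, the nominal day will be used in analysis". A separate fallback deals with dosing: "If there is no pre-dose assessment for the window, then the closest post-dose assessment may be used instead".

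Table 2 places Week 16 at nominal Day 113 with a window of Days 109 to 136 pre-dose. Week 4 (Day 29) runs from Day 1 post-dose to Day 42, Week 8 (Day 57) from Day 43 to 70, and Week 12 (Day 85) from Day 71 to 108.

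SAP 6.2, immediately before, has its own selection statement: "Endpoints analyzing the placebo-controlled data will use the last pre-dose assessment for all visits and for all study arms".

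**The concern.** Table 2 accepts Week 16 counts up to 23 days after the nominal day, and one late unscheduled count is usable. A second late count makes the one-sided rule apply, and then neither qualifies. The post-dose fallback does not help, because it operates only when the window holds no pre-dose assessment. Having more data therefore yields less.

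Where the window opens well before the nominal day, the same rule can pass over a count a day or two late in favour of one taken weeks early. That happens at Weeks 4, 8 and 12, which are repeated-measures time points in the primary model (SAP 7.5.1).

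At stake is which record becomes a subject's primary-endpoint value. A programmer who meets the case must drop an observed count or improvise, and SAP 6.2 and 6.2.1 support different answers. The choice also reaches HiSCR50. A subject without Week 16 data leaves the denominator in SAP 6.2.3 unless non-response can be confirmed from the data available, and counts as a non-responder under protocol 9.4.6.1.

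**Working it through.** **The plan's power figure, as background.** Inputs from protocol 9.2 and SAP 3.5: 36 evaluable per arm, difference 4.9, SD 8.2, two-sided alpha 0.10. The non-centrality is 4.9 / (8.2 × √(2/36)) = 4.9 / 1.933 = 2.535 on 70 degrees of freedom. The two-sample t-test then has 80.7% power, which agrees with the stated 80%.

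**Applying SAP 6.2.1 literally.** Assume the scheduled value is missing and two unscheduled pre-dose counts lie in the window. Nominal days and windows are from SAP Table 2.

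| Visit (nominal day) | Window | Earliest eligible | Latest eligible | Counts on Days | Rule takes | Nearer count |
|---|---|---|---|---|---|---|
| Week 4 (29) | 1 to 42 | 29 − 1 = 28 early | 42 − 29 = 13 late | 3 and 31 | 3 (26 early) | 31 (2 late) |
| Week 8 (57) | 43 to 70 | 57 − 43 = 14 early | 70 − 57 = 13 late | 43 and 58 | 43 (14 early) | 58 (1 late) |
| Week 12 (85) | 71 to 108 | 85 − 71 = 14 early | 108 − 85 = 23 late | 71 and 86 | 71 (14 early) | 86 (1 late) |
| Week 16 (113) | 109 to 136 | 113 − 109 = 4 early | 136 − 113 = 23 late | 110 and 114 | 110 (3 early) | 114 (1 late) |
| Week 16 (113) | 109 to 136 | as above | as above | 116 and 120 | none | 116 (3 late) |

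In the last row, Day 116 alone or Day 120 alone would have been used.

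**Comparing the two SAP statements.** For Days 116 and 120, SAP 6.2 gives Day 120 and SAP 6.2.1 gives nothing. For Days 3 and 31 at Week 4, SAP 6.2 gives Day 31 and SAP 6.2.1 gives Day 3.

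**Scale if Week 16 counts were lost.** On the t-test basis, with assumed losses of 1, 2 or 4 counts per arm (35, 34 or 32 remaining), power falls from 80.7% to 79.7%, 78.6% or 76.4%. The losses are illustrative. The mixed model for repeated measures (MMRM) keeps subjects with earlier visits, so the real effect would be smaller.

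**Check of the remedy.** Taking the pre-dose count nearest the nominal day in either direction selects Days 31, 58, 86, 114 and 116 in the five rows. No in-window pre-dose pair is left without a value, and a farther count never displaces a nearer one.

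**The case against.** The strongest reply is that the case is hard to reach. Protocol 7.3 has a missed visit rescheduled as soon as possible and treats it as missed only if the new date falls in the next visit's window. Day 116 is inside the ±4-day visit window, so an attendance then would ordinarily be the Week 16 visit. A rescheduled visit on Day 120 would still be in the Table 2 window and be used as the nominal visit. The schedule of activities plans no extra AN counts. The problem needs two further attendances with lesion counts, neither recorded as Week 16 and both before the dose. In addition, the MMRM retains subjects without a Week 16 value, imputation and tipping-point analyses are planned, and all unscheduled efficacy data are listed. This stands, and it limits the size of the point. It does not make the rule right.

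A dosing rationale does not rescue the rule. Table 2 already restricts dosing visits to pre-dose values, and Weeks 32, 36 and 40, which have no dose, follow the same rule.

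Four stronger readings are tempting, and the documents do not support them:

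- *The Week 16 count is certainly discarded.* SAP 6.2 offers a competing answer. What the text shows is two rules that can disagree, one of which yields no value.
- *A count weeks early can stand for Week 16.* The earliest eligible day is 109, so the limit is 4 days. The same limit holds from Week 20 to Week 36, and it is 5 days at Week 40.
- *About two thirds of affected subjects lose the value.* Of the 378 pairs of distinct days in the Week 16 window, 253 lie wholly after Day 113 (67%). That counts combinations and is not a probability. It presumes visits spread evenly over a window in which the subject stays undosed. Within the ±4-day visit window it is 6 of 36.
- *The rule governs safety summaries.* SAP 6.6.1 does refer scheduled safety data to 6.2.1. But SAP 7.9 has its own rule for laboratory, ECG and vital-sign data, which takes the most recent unscheduled visit.

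**Conclusion.** The point holds as a defect in a stated rule. Read literally, SAP 6.2.1 can leave Week 16 empty when two valid pre-dose counts exist, and it can prefer a count up to 28 days early (Week 4) or 14 days early (Weeks 8 and 12) to one a day or two late. SAP 6.2 can select a different record, and neither section says which prevails.

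The effect is likely to be small. It needs a missing or out-of-window scheduled value together with at least two unscheduled counts in the same window. The documents give no frequency, so the number of subjects cannot be estimated. A reader might also infer that the primary treatment effect is diluted toward zero. Nothing here shows that: an early count standing for Week 4, 8 or 12 reaches the Week 16 contrast only indirectly, through the MMRM's within-subject correlation.

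The conclusion assumes that the selection sentence is applied as written, and that the pre-dose label in Table 2 means before the dose given at that visit.

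**What to change.** Replace the selection sentence in SAP 6.2.1 with wording such as:

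> Where two or more unscheduled visits fall in one window, the pre-dose measurement nearest the nominal day in either direction (any measurement, if no dose is due at that visit) is taken; a tie goes to the earlier measurement.

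Keep the existing post-dose fallback. Add to SAP 6.2 that its last pre-dose rule does not override this choice among unscheduled visits. Without that line the two sections would still differ, since the new sentence picks Day 116 and SAP 6.2 picks Day 120. Align the cross-reference in SAP 6.6.1 with the unscheduled-visit rule in SAP 7.9.

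The cost is a few sentences in the SAP and the matching derivation code, with no new data. The edit should be made before unblinding, so that the choice of record cannot be influenced by treatment results.
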